### 11.5.2 Listings for Vital Signs

For each study part, all individual vital signs data (including orthostatic measurements) and derivations, such as change from baseline, will be listed. Individual data will be flagged with an "H" or an "L" for values that are higher or lower than their reference ranges, respectively, and subjects with 'substantial' increases or decreases from baseline (as defined in [Section 11.5.1](#)) in systolic BP, diastolic BP and heart rate will be flagged with an 'I' (increase) or 'D' (decrease), respectively. If applicable, data from unscheduled vital signs assessments will also be listed and flagged with a "#" to indicate it will not be used in the summary statistics.

In addition, a separate listing of all vital signs data outside their reference ranges by participant will also be provided.

The reference ranges (from Quotient SOP "The Interpretation of the Electrocardiogram, Vital Signs and Clinical Laboratory Data During Phase I / II Clinical Trials") defined in [Table 11](#) will be used.

**Sponsor/Quotient Sciences Confidential**

**Table 11 Vital Signs Reference Ranges**

Parameter	Lower limit	Upper limit
Systolic BP	90 mmHg	140 mmHg
Diastolic BP	50 mmHg	90 mmHg
Heart rate	45 bpm	100 bpm
Oral Body Temperature	35.5°C	37.5°C
Respiration Rate	10 breaths/min	24 breaths/min

NA=Not applicable

## 11.6 ECGs

For each study part, the details of measurement of supine ECG parameters (i.e., ventricular rate, RR interval, QT interval, QTcF interval, PR Interval, QRS duration, QRS axis, rhythm, interpretation and clinical significance and findings) are described in the study protocol. ECG parameters will be reported in the order given above, i.e., both summary tables and data listings.

Triplicate 12-lead ECGs (2 min apart) will be obtained after the participant has been in the supine position for a minimum of 5 min.

On Day 1 of Parts 1 and 2, telemetry (continuous ECG monitoring) will commence at least 30 min before dosing until at least 12 h post-dose. As this monitoring is for safety purposes alone no data will be recorded in the source, except the start and stop time. If cardiac monitoring shows a potentially significant abnormality, a clinical assessment of the participant including a 12 lead ECG will be performed and treatment given, if appropriate.

### 11.6.1 Summary Tables for ECGs

For each study part and time point where triplicate ECGs are taken the arithmetic mean of the triplicate values for each 12-lead ECG measurement will be computed for each participant. These arithmetic means will then be used to compute the summary statistics for the observed values and for the change from baseline values. If 1 of the 3 measurements is missing, the mean of the 2 non-missing measurements will be used. If 2 measurements are missing, the remaining non-missing value will be used.

ECG data, including change from baseline (mean of single 12-lead measurement, Pre-dose, Day 1 of each dosing period where applicable), will be summarised (i.e., n, mean, SD, median, minimum and maximum) at each post-baseline time point by treatment in Part 2 and by all placebo, all active and each active dose in Part 1 and Part 3.

For each study part, the number and percentage of subjects with normal and prolonged QT intervals corrected for heart rate using Bazett's correction (i.e., QTcB) and Fridericia's correction (i.e., QTcF) and increases in QTcB and QTcF intervals from baseline within the categories defined in [Table 12](#) (based on the International Council on Harmonisation [ICH] E14 guideline [\[5\]](#)) will be summarised by time point and overall. Percentages will be based on the number of subjects with measurements at the relevant time point.

**Sponsor/Quotient Sciences Confidential****Table 12 ICH E14 Ranges for QTcB and QTcF Intervals**

Parameter	ICH E14 Range
QTcF/ QTcB interval	≤450 msec (normal)
	>450 msec
	>480 msec
	>500 msec
Increase in QTcF/ QTcB interval from baseline	≤30 msec
	>30 msec
	>60 msec

**11.6.2 Listings for ECGs**

For each study part, all ECG measurements (i.e., single and mean of triplicate readings) including derivations, such as change from baseline, will be listed.

All ECG measurements will be flagged with an “H” or an “L” for values that are higher or lower than their reference ranges, respectively. If applicable, data from unscheduled ECG assessments will also be listed and flagged with a “#” to indicate it will not be used in the summary statistics.

In addition, for the single values obtained from Single 12-lead measurement, and the mean values calculated from the triplicate ECG values, the number of subjects with increase in QTcF interval from baseline (>30 msec) and with ‘substantial increases’ (>60 msec) will be flagged with ‘I’ and ‘SI’, respectively.

A separate listing of all ECG parameters outside their reference range by participant will also be provided. The reference ranges (from Quotient SOP “The Interpretation of the Electrocardiogram, Vital Signs and Clinical Laboratory Data During Phase I / II Clinical Trials”, except QT interval which is from the eCRF) defined in [Table 13](#) will be used.

Additionally, for Part 1 and Part 2 only, the telemetry start and stop times, as well as the nature of any potentially significant abnormality will be listed.

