#### **14.9 Telemetry (Continuous ECG)**

On Day 1 of Parts 1 and 2, telemetry (continuous ECG monitoring) will commence at least 30 min before dosing until at least 12 h post-dose. As this monitoring is for safety purposes alone no data will be recorded in the source, except the start and stop time. If cardiac monitoring shows a potentially significant abnormality, a clinical assessment of the participant including a 12-lead ECG will be performed and treatment given, if appropriate.

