##### **11.4.1 Summary Tables for Laboratory Evaluations**

For each study part, haematology, coagulation and clinical chemistry data will be summarised (n, mean, SD, median, minimum and maximum) for each laboratory parameter at each time point, including changes from baseline (Admission, Day-1) at each scheduled post-baseline time point by treatment in Part 2, and by all placebo, all active and each dose level in Part 1 and Part 3.

Shift tables from baseline to each scheduled post-baseline time point (with respect to the number and percentage of subjects with values below, within or above the reference range) will be presented by treatment in Part 2, and by all placebo, all active and each dose level in Part 1 and Part 3. Percentages will be based on the number of subjects with measurements at baseline and the relevant post-baseline time point.

For fasting-sensitive laboratory parameters (i.e., glucose) results taken in the non-fasted state (i.e., LBFAST=N) will not be included in summary statistics by time point or be used in derivations of changes from baseline. For tabulations (e.g., shift tables) both fasted and non-fasted results will be pooled and used in the tabulations, using the appropriate fasted or non-fasted reference range. All results (fasted or non-fasted) will be listed with non-fasted data flagged.

Reference ranges for each laboratory parameter will be presented for the relevant parameter in each summary table.

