##### **11.4.2 Listings for Laboratory Evaluations**

For each study part, the sample collection data (e.g., collection times) for laboratory analysis and urinalysis data will be listed.

All individual participant data, for planned haematology, clinical chemistry and urinalysis data including derivations, such as change from baseline, will be listed. If applicable, data from unscheduled laboratory tests will also be listed and flagged with a "#" to indicate it will not be used in the summary statistics. In these listings, individual data will be flagged with an "H" or an "L" for values that are higher or lower than their reference ranges, respectively.

Separate listings of all haematology, coagulation, clinical chemistry and urinalysis values outside their reference ranges by participant will also be provided. Reference ranges will be supplied by the safety laboratory for haematology and clinical chemistry and per the eCRF for urinalysis (i.e., a positive or negative result) with the exception of the following reference ranges for urinalysis:

- pH: 5.0 to 9.0

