**Sponsor/Quotient Sciences Confidential**

Table Number	Table Title
	Vital Signs and ECG Results
14.5.1.1	Vital Signs Summary Statistics: Safety Analysis Set Part 1 Parameter <units>
14.5.2.1.1	ECGs Summary Statistics: Safety Analysis Set Single 12-Lead Part 1 Parameter <units>
14.5.2.1.2	ECGs Summary Statistics: Safety Analysis Set Mean of Triplicate 12-Lead Part 1 Parameter <units>
14.5.2.1.3	ECGs QTcB and QTcF Categorical Data Summary Statistics: Safety Analysis Set Part 1
14.5.1.2	Vital Signs Summary Statistics: Safety Analysis Set Parameter <units> Part 2
14.5.2.2.1	ECGs Summary Statistics: Safety Analysis Set Parameter <units> Single 12-Lead Part 2
14.5.2.2.2	ECGs Summary Statistics: Safety Analysis Set Mean of Triplicate 12-Lead Parameter <units> Part 2
14.5.2.2.3	ECGs QTcB and QTcF Categorical Data Summary Statistics: Safety Analysis Set Part 2
14.5.1.3	Vital Signs Summary Statistics: Safety Analysis Set Part 3 Parameter <units>

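### Unscheduled readings are left out of the QTc, laboratory-shift and vital-sign counts, so those tables can undercount participants who crossed a threshold

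*SAP*

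**What the plan says.** The same rule appears three times in the SAP listing sections.

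- Laboratory (SAP 11.4.2): "data from unscheduled laboratory tests will also be listed and flagged with a" hash sign.
- Vital signs (SAP 11.5.2): "data from unscheduled vital signs assessments will also be listed and flagged with a" hash sign.
- ECGs (SAP 11.6.2): "data from unscheduled ECG assessments will also be listed and flagged with a" hash sign.

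In each case the stated purpose of the flag is "to indicate it will not be used in the summary statistics".

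The counts at issue are defined in the companion summary sections. SAP 11.4.1 specifies "Shift tables from baseline to each scheduled post-baseline time point". SAP 11.5.1 counts participants with substantial changes in blood pressure and heart rate, and with substantial supine-to-standing falls. SAP 11.6.1 says the QTcF/QTcB categories and increases "will be summarised by time point and overall".

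The protocol expects unscheduled readings. Under Protocol 14.9, "If cardiac monitoring shows a potentially significant abnormality, a clinical assessment of the participant including a 12-lead ECG will be performed". Protocol 14.5.10, 14.6, 14.7 and 14.13 allow repeat or additional laboratory tests, vital signs and ECGs, and Protocol 8.3 asks for a repeat to confirm the QTcF and ALT criteria.

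**The concern.** Safety is the primary objective. The QTc categories, shift tables and substantial-change counts are the outputs a reader will use to see whether anyone reached an extreme value. For-cause readings are taken because something already looks abnormal. If such a reading is the only one to cross a threshold, the tables as specified place that participant in the category given by the scheduled values. The ECG table cut-offs of >500 msec and >60 msec (Protocol Table 10, SAP Table 12) also appear in Protocol 8.3 and 8.5, so a difference between the table and what was seen during the study would be awkward to explain in the report.

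The telemetry case is the clearest. Protocol 14.9 keeps nothing from telemetry in the source except start and stop times, so the ECG it prompts is the measured record of the event in the safety dataset. The Holter results are reported separately, outside the CSR (SAP 3.1).

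**Working it through.** **The plan's own figure.** The only sample-size figure is the chance of at least one AE among 6 active participants (Protocol 15.1, SAP 5.3), which is 1 − (1 − p)^6. For p = 10%, 15%, 20% and 25% this gives 46.9%, 62.3%, 73.8% and 82.2%, matching the stated 47%, 62%, 74% and 82%. The point does not depend on it, but it fixes the planned denominator at 6.

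**Does the rule reach each count?**

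| Count | Text that decides it | Unscheduled post-dose values used? |
|---|---|---|
| QTcF/QTcB categories and increases | SAP 11.6.2 flag; table titled "ECGs QTcB and QTcF Categorical Data Summary Statistics: Safety Analysis Set Part 1" in the SAP 18 index | No, as written |
| Laboratory shifts | SAP 11.4.1 limits shifts to scheduled time points (tables are titled Shift Analysis, so the title does not decide it) | No |
| Substantial vital-sign changes | SAP 11.5.2 flag; counts are columns of Tables 14.5.1.1 and 14.5.1.2, titled Summary Statistics | No, as written |

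SAP 14.1 allows an unscheduled value to stand in for a missing baseline. That is the only exception found, and it brings no post-dose reading back. No any-time or worst-value rule appears elsewhere.

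**The undefined overall count.** SAP 11.6.1 promises one, but its percentages are based on participants measured at the relevant time point, which gives an overall count no denominator. Mock Tables 14.5.2.1.3 and 14.5.2.2.3 show baseline and time-point rows only.

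**Direction of the effect.** Let S be a participant's scheduled readings and U the unscheduled ones. Since max(S) ≤ max(S and U together), a count of participants ever above a threshold can only stay the same or fall when U is dropped. Two cases need separating:

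1. A scheduled reading crosses and the repeat is unscheduled: the participant is already counted, so dropping the repeat changes nothing.
2. No scheduled reading crosses but an unscheduled one does: the participant is missed.

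Only case 2 is a loss.

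**Size of one missed participant (100/n).**

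| Group | n | Percentage points |
|---|---|---|
| Planned active dose group | 6 | 16.7 |
| Minimum active group (Protocol 8.1.1) | 4 | 25.0 |
| Part 2 | 8 | 12.5 |
| Pooled Part 1 placebo, 4 or 5 cohorts | 8 or 10 | 12.5 or 10.0 |
| Pooled Part 1 active, 4 or 5 cohorts | 24 or 30 | 4.2 or 3.3 |

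**Illustration only.** Assume an excursion of fixed length D lies at random within the 12 h telemetry window, with Part 1 post-dose ECGs at 0.5, 1, 2, 3, 4, 5, 6, 8 and 12 h (Protocol Appendix 5). The share touching no scheduled ECG is the sum over intervals of max(0, interval length − D), divided by (12 − D):

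- D = 0.5 h: (5×0.5 + 1.5 + 3.5)/11.5 = 7.5/11.5 = 65%
- D = 1 h: (1 + 3)/11 = 36%
- D = 2 h: 2/10 = 20%

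This shows that case 2 is possible for short excursions. It says nothing about how often excursions occur.

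**The case against.** The strongest reply is that little is hidden. Unscheduled values are listed, out-of-range values have their own by-participant listings, QTcF increases above 30 and 60 msec are flagged, and telemetry abnormalities are listed (SAP 11.4.2, 11.5.2, 11.6.2). Clinically significant abnormalities must be reported as AEs (Protocol 14.5.10, 14.6, 14.7), and AEs are tabulated. With 6 active participants per dose, reading the listings is practical. All of this stands, and it limits the point to the counts.

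A second reply is that the reach of the flag to category counts is not beyond doubt: SAP 11.4.1 itself contrasts by-time-point summary statistics with tabulations such as shift tables. The table titles point the other way, and the shift tables are limited explicitly. The missing overall row is weak evidence alone, because the shells are abbreviated and SAP 16 lets them be modified. At the least, the wording needs settling.

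A reader might go further and infer that someone who met a withdrawal or pausing criterion could vanish from the report's tables. The documents do not support that. Each numeric pausing rule in Protocol 8.5 needs at least two participants. The study-drug withdrawal criteria in Protocol 8.3 apply to Parts 2 and 3 and are framed as serious or severe AEs, which SAP 11.3.1.1 tabulates, along with TEAEs leading to withdrawal.

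A reader might also take the schedule gaps (for example 72 h between the 24 h and 96 h laboratory samples in Part 1) or the dog heart-rate effect from 2 to 20 h as a measure of what is lost. They are not. The gaps are design features. The heart-rate effect was at 1000 mg/kg only, and the same study found no statistically significant QT or QTc effect (Protocol 5.3.1.3). Telemetry is required only to at least 12 h, and Holter recording to at least 24 h feeds the safety committee's review (Protocol 14.8).

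**Conclusion.** The point holds as a possible undercount in the categorical safety tables. As written, a participant whose only crossing is on an unscheduled post-dose reading is classified by scheduled values in the QTcF/QTcB, laboratory-shift and substantial-change tables. One such participant moves a planned dose group from 16.7% to 0%, and Part 2 from 12.5% to 0%. This assumes that the flag in SAP 11.5.2 and 11.6.2 covers counts in tables titled Summary Statistics, and that the triggering reading itself is unscheduled. The telemetry route applies to Parts 1 and 2; for-cause repeats can occur in any part. The documents give no basis for a frequency. Separately, the overall QTc count in SAP 11.6.1 needs a definition and a denominator in any case. The appropriate weight is that of a cheap improvement.

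**What to change.** Keep all by-time-point statistics on scheduled data, and make these changes:

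- **SAP 11.6.1 and Tables 14.5.2.x.3:** define the overall count as each participant's highest post-dose QTcF and QTcB, and largest increase from baseline, over all scheduled and unscheduled readings, per treatment (per period in Part 2). The denominator is participants with any post-dose reading (and a baseline, for increases). Add the row to the shells.
- **SAP 11.4.1 and 11.5.1, with Tables 14.4.x.2, 14.4.x.4 and 14.5.1.x:** add separate any-post-dose high (or increase) and any-post-dose low (or decrease) counts on the same basis. A single worst-value row would not work, because these outputs run in two directions and one participant can be extreme in both. For orthostatic falls, add one any-post-dose fall count.
- **SAP 11.4.2, 11.5.2 and 11.6.2:** restrict the flag's meaning to by-time-point summaries.
- **Footnote:** participants with more readings have more chances to show an extreme value, and for-cause readings may be taken under non-standard conditions, so comparisons between groups need care.

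The cost is SAP wording, a few extra rows and the matching programming. No new data are needed.

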**Table 13 ECG Reference Ranges**

Parameter	Lower limit	Upper limit
Ventricular Rate (HR)	45 bpm	100 bpm
QT Interval	200 msec	600 msec
QTcB/QTcF Interval	NA	450 msec
PR Interval	120 msec	210 msec
QRS Duration	NA	120 msec
QRS Axis	-30°	100°

HR=heart rate

NA=Not applicable

**11.7 Body Weight**

In Part 1 and Part 3, all body weight data will be listed.

**Sponsor/Quotient Sciences Confidential**

---

## **11.8 Physical Examination**

All physical examination and targeted physical examination details and comments on any findings will be listed by participant for all subjects.

## **12 Interim Statistical Analyses**

No interim statistical analysis is planned for this study.

## **13 Changes in the Conduct of the Study or Planned Analysis**

### **13.1 Changes in the Conduct of the Study**

No changes in the conduct of the study had been reported at the time this document was written.

### **13.2 Changes to the Planned Analyses**

No changes to planned analysis.

### **13.3 Any Other Relevant Changes**

Not applicable.

## **14 Overall Considerations**

### **14.1 Statistical Programming and Analysis**

The Data Sciences Department at Quotient will perform the statistical programming and analysis to produce all analysis datasets and TFLs using the statistical SAS Software v9.4.

In general terms, categorical data will be presented using counts and percentages, while continuous variables will be presented using n, mean, SD, median, minimum and maximum. For PK data additional statistics including CV%, geometric mean, geometric SD and geometric CV% will be presented, as appropriate.

The geometric mean is obtained by applying a natural log transformation to the raw data, calculating the arithmetic mean of the transformed values and then back transforming the arithmetic mean.

The following formula will be used to calculate the geometric SD:

$$\text{geometric SD} = \exp\{\text{SD}[\log(\text{raw data})]\}$$

ie, a natural log transformation is applied to the raw data, the arithmetic SD of the transformed values is calculated, and then the arithmetic SD of the transformed values is back transformed.

The following formula will be used to calculate the geometric CV%:

$$\text{geometric CV\%} = 100 \times (\exp\{\text{SD}[(\log(\text{raw data}))^2 - 1]\})^{1/2}$$

ie, a natural log transformation is applied to the raw data, the arithmetic SD of the transformed values is calculated. This value is then squared. The square value is back transformed and a value of 1 is subtracted from the back transformed value. A square root is then applied and the resulting value is multiplied by 100.

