#### **5.3 Study Sample Size**

For Parts 1 and 3, the primary objective is an initial assessment of safety and each treatment group is therefore limited to 6 participants receiving active IMP. Administration of MMV367 to 6 participants at each dose level provides a 47%, 62%, 74%, or 82% probability of observing at least 1 occurrence of any AE, with a true incidence rate for a given dose group of 10%, 15%, 20%, or 25%, respectively.

Furthermore, it is assumed that pooling the data for the 2 participants who receive placebo in each cohort will provide an adequately sized control group to assess a possible drug effect on safety laboratory tests, vitals and ECG parameters.

Part 2 is a pilot evaluation designed to determine whether MMV367 PK is impacted by high-fat food. Historically, 8 participants have proven sufficient to characterise the preliminary effects of food on safety and PK of a new chemical entity in healthy participants. Therefore, a sample size of 8 is considered adequate at this stage of drug development.

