### **9.3 Concentration and PK Parameter Summary Tables**

Summary statistics (i.e., n, mean, SD, CV%, median, minimum, maximum, geometric mean, geometric SD and geometric CV%) of concentration data will be calculated for each time point and treatment for MMV367 in plasma. The number of BLQ values (n#) per time point will also be presented. Geometric statistics will not be calculated for Day 1, pre-dose concentrations.

Summary statistics (i.e., n, mean, SD, CV%, median, minimum and maximum) of plasma PK parameters will be calculated for MMV367 for each treatment and day (where appropriate). Geometric mean, geometric SD and geometric CV% will be presented for all plasma PK parameters except Tmax.

In Part 1, Cohort 1C and 1D, should a validated method be developed, and the urine concentrations be required to be reported by Quotient in Part 1, urine Ae and CumAe will be summarised using the n, mean, SD, CV%, median, minimum, and maximum) whilst %Ae and Cum%Ae will be summarised using the n, mean, SD, CV%, median, minimum and maximum only.

Non-measurable values reported in the plasma concentration data (i.e., values that are BLQ), will be entered as zero for the determination of summary statistics with the exception of geometric means, geometric SD and geometric CV%, where BLQ values will be imputed as half the lower limit of quantification (LLOQ) value. This also applies to any concentrations that are defined as PK parameters. Data recorded as NR, NS or NC will be handled as missing (i.e., no assumption will be made about the actual concentration).

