### **9.6.2 Part 2: Assessment of Food Effect**

Formal statistical analysis will be performed on the PK parameters Cmax, AUC(0-last) and AUC(0-inf), to assess the presence of a food effect. The null hypothesis is that there is no difference between fed and fasted treatments.

The PK parameters will undergo a natural logarithmic transformation and will be analysed using mixed effect modelling techniques. The model will include terms for fed/fasted status and period fitted as fixed effects and participant fitted as a random effect.

Only subjects who complete both the fed and fasted periods will be included in the statistical analysis. Furthermore, for AUC(0-inf) only, a participant must have reliable estimates of AUC(0-inf) for both fed and fasted periods to be included in the statistical analysis. If the number of subjects with reliable estimates for both periods is less than 4 (i.e., less than 50% of planned number of evaluable subjects) then no formal statistical analysis of AUC(0-inf) will be performed i.e., descriptive summaries only.

The adjusted means including differences from the fed/fasted comparison and the associated 90% CIs obtained from the model are back transformed on the log scale to obtain adjusted geometric mean ratios (GMRs) and 90% CIs of the ratio. These will be presented together with the p-value from the fed/fasted comparison.

The fixed effects table from the model with F-statistic and p-value for the relevant effects will be presented in a separate table.

The intra-participant variability values will be calculated for all treatments combined and are obtained from the residual term from the SAS Software output. These values are calculated as follows:

$$CVw = 100 \times (\exp(\text{Mean Square Error}) - 1)^{1/2}$$

The analysis will be performed using the SAS Software procedure PROC MIXED, the method will specified as Restricted Maximum Likelihood and the denominator degrees of freedom for the fixed effects will be calculated using Kenward-Roger method [4]. The following is an example of the SAS Software code that will be used:

```
PROC MIXED DATA= METHOD=REML ORDER=INTERNAL;
  CLASS SUBJIDN FSTATUS APERIODN;
  MODEL LVAR = FSTATUS APERIODN / OUTP=PRED DDFM=KR;
  RANDOM SUBJIDN;
  ESTIMATE <relevant pairwise treatment comparisons> / CL ALPHA=0.10;
  LSMEANS TRTAN / ALPHA=0.10;
  LSMEANS=MEANS ESTIMATES=EST COVPARMS=CVW;
RUN;
```

where

- LVAR is the natural log transformed PK parameter of interest

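### The displayed geometric CV% formula in SAP 14.1, as it reads in the extracted text, contradicts the step-by-step definition beneath it and should be corrected once checked against the source PDF

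*SAP*

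**What the plan says.** SAP 14.1 (Statistical Programming and Analysis) introduces the statistic with "The following formula will be used to calculate the geometric CV"%. In the displayed equation the square is attached to the logged data, the subtraction of 1 sits inside the SD bracket, and the SD is in turn inside the exponential.

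The explanation that follows, offered as a restatement, has a different order of operations. After the log transformation, "the arithmetic SD of the transformed values is calculated. This value is then squared". Next, "The square value is back transformed and a value of 1 is subtracted from the back transformed value". Finally, "A square root is then applied and the resulting value is multiplied by 100".

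SAP 9.6.2 gives a sister formula for within-participant variability, CVw = 100 × (exp(Mean Square Error) − 1)^(1/2), with the 1 subtracted outside the exponential.

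On use, SAP 9.3 states "Geometric mean, geometric SD and geometric CV% will be presented for all plasma PK parameters except Tmax". It also applies geometric statistics to plasma concentrations at each time point, except Day 1 pre-dose. Tables 5 and 6 leave the lambda-z lower and upper limits out of the descriptive statistics, and express concentrations and AUCs in an unspecified mass unit.

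**The concern.** The plan gives two definitions of one reported statistic and presents them as equivalent. The displayed one is introduced as the rule to be applied. A programmer and a checker who each relied on a different half of the same paragraph would get different columns in the PK summary tables of all three parts. PK is a secondary objective, and these columns are its descriptive measure of between-participant spread.

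**Working it through.** The documents state no numerical geometric CV%, so there is no figure to reproduce. The check compares the two definitions.

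**Definitions.** Let y = ln(x).
- Words: 100 × sqrt(exp(SD(y)²) − 1).
- Display, literally: 100 × sqrt(exp(SD(y² − 1))).

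**Three properties of the literal display.**
1. Subtracting a constant inside an SD changes nothing, so SD(y² − 1) = SD(y²) and the 1 has no effect.
2. An SD is at least 0, so the exponential is at least 1 and the result is at least 100%. Six identical values give 100%; the words give 0%.
3. Changing the unit by a factor k adds c = ln(k) to each y. Since (y + c)² = y² + 2cy + c², the SD changes through the 2cy term. SD(y) itself does not change, so the worded version is free of units.

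**Size, large-sample.** Inputs: predicted exposures at 300 mg from protocol Table 2 (Cmax 2.2 µg/mL, AUC(0-inf) 55.5 µg.h/mL), used as geometric means. The true geometric CV of 30% is an assumption, giving s² = ln(1 + 0.30²) = ln(1.09) = 0.08618. For normal y with mean m and variance s², Var(y²) = 4m²s² + 2s⁴.

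| Case | m = ln(geometric mean) | Var(y²) | SD(y²) | Literal display | Words |
|---|---|---|---|---|---|
| Cmax 2.2 µg/mL | 0.7885 | 0.2291 | 0.4787 | 127.0% | 30% |
| AUC 55.5 µg.h/mL | 4.0164 | 5.5755 | 2.3612 | 325.6% | 30% |
| Cmax 2200 ng/mL | 7.6962 | 20.4327 | 4.5202 | 958.4% | 30% |

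The literal column is 100 × exp(SD(y²)/2). Simulating 1,000,000 lognormal values gave 127.0%, 325.8% and 957.6%.

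**Size at n = 6, over a range of spread.** Six is the planned active group size ("Administration of MMV367 to 6 participants at each dose level", SAP 5.3). Six normal-score values were scaled to an assumed log-SD around the predicted 100 mg AUC(0-inf) of 18.8 µg.h/mL (protocol Table 2).

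| Assumed log-SD | Words (any unit) | Literal, µg.h/mL | Literal, ng.h/mL |
|---|---|---|---|
| 0.1 | 10.0% | 134.1% | 267.6% |
| 0.2 | 20.2% | 179.9% | 715.9% |
| 0.3 | 30.7% | 241.4% | 1915.9% |
| 0.5 | 53.3% | 435.5% | 13729.4% |
| 0.8 | 94.7% | 1064.5% | 264037.6% |

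For the predicted 100 mg Cmax of 0.7 µg/mL at log-SD 0.3, the literal display gives 112.1% in µg and 714.0% in ng; the words give 30.7% in both.

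**Consistency with CVw.** Putting MSE = 0.3² = 0.09 into the 9.6.2 formula gives 100 × sqrt(exp(0.09) − 1) = 30.7%, the same as the words.

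**The case against.** The strongest reply concerns provenance. The fault lies entirely in where a superscript and some brackets fall, in an equation rebuilt by a program from a PDF. The neighbouring geometric SD formula and the CVw formula came through sensibly, which is some reassurance but does not rule out an extraction fault here. This stands, and it makes the point conditional on a look at the PDF.

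The second reply is that the intended definition is already in the plan, because the words are complete and unambiguous. This also stands. What remains is a wrong display under a lead-in that makes it operative.

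Third, SAP 14.2 requires peer review of SAS code and 14.2.1 requires manual checks of summary tables, so a column that never falls below 100% would probably be noticed. That is likely, unless the checker uses the same display. Interim PK summaries are exported from WinNonlin (SAP 9.7), not from the SAS outputs.

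A reader might also infer more than the documents support:
- *That the reported variability will be wrong.* This happens only if someone codes the display and ignores the words.
- *That the literal formula always inflates.* For the exposures examined it does; in 20,000 simulated samples of six (geometric mean 18.8, log-SD 0.3) it exceeded the worded value every time. It is not an algebraic certainty. Six log values alternating between +1.5 and −1.5 give 100% literally and 372.6% from the words.
- *That the error amounts to exp(SD² − 1).* That reading gives 63% when the truth is 30%, but it is not what is displayed.
- *That every concentration and PK parameter is affected.* Day 1 pre-dose concentrations, Tmax and the lambda-z limits are outside it.
- *That later studies would be mis-sized.* The documents do not say these figures will be used for sizing.

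**Conclusion.** The point holds as a minor correction, on the extracted text. The display and the words in SAP 14.1 define different quantities, and the words give the standard one. Literal use would produce unit-dependent figures with a floor of 100%. The 127%, 326% and 958% illustrations depend on the assumed 30% CV and on the protocol's predicted exposures; the floor and the unit dependence do not depend on either.

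The reach is descriptive only: geometric CV% for plasma concentrations and plasma PK parameters, with the exceptions noted. The dose-proportionality power model, the fed/fasted ratio with its confidence interval, and CVw are untouched, and the primary endpoints are safety endpoints. If the source PDF already has the brackets in the right place, there is no finding.

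**What to change.** First confirm the bracket positions against the source PDF. If they are as extracted, replace the display in SAP 14.1 with: geometric CV% = 100 × (exp{(SD[log(raw data)])²} − 1)^(1/2). Leave the explanatory words as they are.

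The cost is a one-line SAP correction. It changes no intended analysis and needs no new data or output, and it gives the programmer and the checker a single definition.
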